The task will be set up by the facilitator and will give the trainee standardised instructions and a short demo video on how to perform this task (**Appendix 7**). The task begins when the trainee inserts the camera to find the character on the first target (e.g. **1**), zoom in and identify the small size character (e.g. **a**) located next to it. Before they can proceed to the next target, the facilitator needs to confirm that they are happy with the identification and placement of the small character by saying "next". Trainee can demonstrate this by placing the target in the circle on the screen and reading it out. Trainee can then navigate the camera to find the next target on the LASTT model which in the above example will be large character '**A**', then zoom in to find the small character next to it, put the small character in the circle on the screen and read it out. They can then move on when indicated by faculty as ok to do so. Trainee can then continue until they find the 14th target "**N end**" which completes the task. Please see figure 1 for an example. The facilitator will record the trainee's study number (badge number) and time taken to identify 14 targets. A time of 2 minutes and 30 seconds is considered as ideal for completion of this task. If trainee exceed this time then it will incur a penalty. For every

30 seconds they exceed beyond 2 minutes and 30 seconds, 1 target will be subtracted from the total number of targets they have found. The penalty column does not need to be completed at the time of assessment and can be worked out retrospectively. Furthermore maximum time allowed for this task is 5 minutes and if all 14 targets have not been identified within 5 minutes then the trainee is encouraged to move on to the second sequence of this task, i.e. round 2. The assessor will be required to record the last target found on the evaluation sheet if 5 minutes limit is reached and the task is still incomplete. The rationale for the 5 minute cap is to minimise fatigue. This task will be repeated 3 times and above data will be recorded on the evaluation sheet (**Appendix 8**). To avoid memory effect the sequence of targets will be changed each round so that there are 3 different sequences to find. The same 3 sequences will be used for all trainees throughout the testing phase (**please see the end of appendix 7**).

Task 2 - Hand eye co-ordination (HEC)

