To assess HEC, trainees are assessed on their ability to transfer objects as well as navigate the camera. The trainee is expected to use the dominant hand (DH) to hold grasping forceps and non-dominant hand (NDH) to hold the camera. The LASTT model will be used to assess this.

The facilitator will set up the Szabo box trainer for this task. Coloured cylinders will be placed (10 × 4-mm open cylinders) in a circular style in a vertical upright position around the “+he academy...” sign on the LASTT model. There will be 2 cylinders of each colour in case one is dropped out of view. Corresponding coloured targets, i.e. nails (10 × 1 mm) will be located in easy view on the LASTT model. Facilitator will place 1 lateral port so that the coloured cylinders and LASTT model can be comfortably reached. The facilitator will give standardised instructions and show a standardised demonstration video on how to perform this task (**Appendix 7**).

The trainee is expected to insert the 10mm 0 degrees camera through the central port of Szabo box trainer. The time starts when the trainee inserts the grasper through the lateral port and the grasper comes into endoscopic view. The trainee is expected to identify a coloured cylinder (e.g. green), grasp it with Maryland forceps using their DH and transfer it to the corresponding coloured nail whilst using NDH to drive the camera. Once the cylinder is correctly placed over the pin, the trainee can proceed to the next coloured cylinder and continue until 3 minutes have elapsed or all the 6 cylinders have been transferred. If a cylinder is dropped the trainee can re grasp it if possible or choose to use the second cylinder of the same colour provided it is still in endoscopic view. All grasped then dropped cylinders will also be recorded. This task will be repeated 3 times and scores for each run will be recorded on the task evaluation sheets (**Appendix 8**). The time taken for the trainee to transfer 6 objects correctly will be recorded (if completed in 3 or less minutes) or if the task is incomplete in 3 minutes, then the total number of cylinders transferred will be counted. To avoid memory effect the colour sequence of targets will be changed each round. The same 3 sequences will be used for all trainees throughout the testing phase (**please see the end of appendix 7**).

Task 3 - Bimanual co-ordination (BMC)

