Trainees will be expected to place interrupted sutures between two dots and perform 4 intra corporeal knots with 3 throws. They will be instructed to place sutures between the two dots along the first 4 rows on the foam pad. The trainee is not expected to use the 5th row at the bottom of the foam pad. A total of 15 minutes will be allowed for this task and the time taken to complete 4 sutures and 4 knots if performed will be recorded. If the trainee runs out of time, then total number of sutures +/- knots performed within the 15 minutes will be recorded. At the completion of the tasks, each foam pad will be labelled with the trainee's study number and collected. The quality of suturing and knot will be assessed after completion of the task using validated SUTT scoring system by two independent assessors **(Appendix 9)**.

Measurement of EMG and EEG

Musculoskeletal and cognitive fatigue will be tested using electromyography (EMG) and electroencephalography (EEG) respectively in a sub set of trainees as described earlier. They will be fitted with EMG and EEG electrodes as per the protocol and this data will be collected for round 2 of tasks 1-3 and throughout the duration of the suturing task 4. As the equipment is wireless, it is anticipated that the trainee's freedom of movement will not be affected by it. EMG will be measured by placing wireless electrodes over arms, neck and upper and lower back muscles **(Appendix 10)** and EEG will be recorded using wireless electrodes over the scalp using a validated protocol **(Appendix 11)**.

Location and timescale for experiments

We have opted to conduct these tasks in a large seminar/conference room to minimise any potential pressure on performance of another colleague. We are restricting the number of trainees to a maximum number of 6 per each run. We will conduct these tasks over 3 weekends (2 consecutive weekends and one weekend 3 weeks later). The rationale behind this is to increase the chances of recruiting volunteers who may be restricted otherwise by on-call commitments or might be away on leave.

Choice of location will be between Royal Blackburn hospital and Manchester based hospitals.

Outcome measures

The primary outcome measure:

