--------------------	-------------------	--------------	-------------------	---------------	-------------------------

Q6. In which training grade were you **initially** allocated to an operative laparoscopy list?.....

Q7. How regularly are you allocated to a theatre list involving operative laparoscopy? Please tick one of the following statements.

>2 times per week.	2 times per week.	Once weekly.	Once fortnightly.	Once monthly.	Less than once monthly.
--------------------	-------------------	--------------	-------------------	---------------	-------------------------

Q8. When allocated to a theatre list involving operative laparoscopy, do you '**Generally**' get the opportunity to perform some or most of the operation in suitable training cases, or are you mostly assigned as an assistant or an observer? Please tick one of the following statements or free text your answer if you are able or want to provide more details.

I get the opportunity to perform some or most of the operation in cases suitable for training.	I am usually assigned to an assistant's role.	I usually observe the case only.	
--	---	----------------------------------	--

Space for free text answer.-----

Q9. How frequently were you involved in emergency operative laparoscopy such as lap appendicectomy, cholecystectomy, laparoscopic management bowel obstruction, of ectopic pregnancy and or ovarian torsion? Please tick one of the statements below.

>2 times per week.	2 times per week.	Once weekly.	Once fortnightly.	Once monthly.	Less than once monthly.
--------------------	-------------------	--------------	-------------------	---------------	-------------------------

Physical health and fitness:

What form of regular exercise do you undertake? E.g. Walking/running/resistance training/yoga etc

.....

How frequently do you undertake the above exercise in a week? Please choose by ticking the appropriate statement from the list below.

Activity level

Inactive (less than 30minutes a week)	
Moderately Active (Between 30 and 60 minutes a week)	
Active (Between 60 and 150 minutes a week)	

Musculoskeletal symptoms

During the past 12 months have you had any trouble (ache/pain/discomfort/numbness) in any of the following please: (please circle the appropriate response)

Body system	Yes	No
Neck		
Right shoulder		
Left shoulder		
Right wrist		
Left wrist		
Right upper back		
Left upper back		
Right lower back		
Left lower back		

Appendix 7

Trainee Instructions for laparoscopic tasks

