Grasp the plastic head of the pin with Johan forceps using your non-dominant hand and lift the pin up.

Whilst elevated, pass the pin to the dominant hand by grasping the metal part of the pin with a Maryland grasper.

Place the pin (head or tail) in the corresponding coloured disc and repeat for all colours. Once the pin is positioned in the disc of the same colour, you may move on to the next coloured push pin. It is not necessary to position the entire length of the pushpin in the respective circle. You may use both hands to stop the pin from falling out.

You are only required to place 6 pins in their respective circles, i.e. one of each colour. If the pin is dropped, use the second pin of the same colour or you may re-grasp the fallen pin, as long as you can find the pin within the endoscopic boundaries.

This task will be repeated 3 times with 3 different colour sequences.

Exercise 4: Suturing and knot tying

The aim of this task is to perform 4 interrupted stitches using correct needle handling and intra-corporeal knot tying techniques.

Perform 4 interrupted sutures by taking a needle bite through the black dots in a horizontal plane. Please use the first 4 rows for your sutures and leave the 5th row.

Pass the suture by entering and exiting precisely within the black dots.

Perform an intra-corporeal knot with 3 throws. Ensure that the knot is secure.

Cut the excess suture using laparoscopic scissors leaving behind a tail of approx. 1-2cm.

[figure not shown]
The link to the video demonstration for tasks 1-3 is:

<https://europeanacademy.org/training-tools/lastt/>

[figure not shown]
The link to suturing demonstration video is:

<https://www.youtube.com/watch?v=2qCBvbWBJ64>

[figure not shown]
Below are the 3 different sequences to be used in task 1.

Sequence 1

Sequence 2

Sequence 3

The following are 3 different colour sequences to be used in task 2 and 3.

Colour sequence 1 for tasks 2 and 3

Colour sequence 2 for tasks 2 and 3

Colour sequence 3 for tasks 2 and 3.

Appendix 8

Task evaluation sheets for laparoscopic tasks

Please indicate the time as you read it on the stopwatch in MM:SS:HH

Task 1: Laparoscopic Camera Navigation (LCN)

Runs	Time required for identifying all 14 targets. (If within or up to 5 minutes taken).	If 5 minutes are exceeded, record the last found target (small character).	Penalties. To be filled after study tasks are completed.
1	: :		
2	: :		
3	: :		

Task 2: Hand- Eye Co-ordination (HEC)

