Place the LASTT model in the box such that the top edge of this box is lined up with the second white pin along the side of box trainer. Put the inserts as per sequence 1.

A 10mm and 30 degrees camera is used. It is to be inserted through the most proximal central port on the Szabo box trainer. Request the trainee to read the instructions and then show them the demonstration video.

Check trainee's understanding of the task.

On the LASTT model there are 14 targets. Each target consists of a large character and a small character (numbers and alphabet letters).

The task time begins when the trainee inserts the camera to find the first target. The small character on that target indicates their next target.

The first target is always '1a'. Trainee starts their search by locating the first target "1a". The figure below is an example of what the first target looks like.

Large character '1' corresponds to the starting character.

Small character 'a' corresponds to the next character to find which will appear as a large character on the subsequent target.

Once the small character is found, trainee needs to zoom in and place the small character in the circle on the screen. If you approve that the entirety or boundaries of the small character is placed in the circle on the screen then indicate that they can move on to next target by saying 'next.' The trainee should now navigate the camera to find capital 'A' on the next target, then zoom in, find the small character next to it

and place it in the circle on the screen and then move on. The trainee can continue until all 14 characters have been found indicated by finding 'Nend'. This completes the task.

Record the time taken to find 14 targets for each round. Ideal time for completing this task is 2 minutes and 30 seconds. However we are allowing a maximum time of 5 minutes for its completion. If trainee is unable to complete the task within 5 minutes, then stop the trainee at that point and record the last target they found; e.g. Mq.

Now change the inserts for round 2 using sequence 2 and repeat above. Record the same data as above before proceeding to round 3 using sequence 3. Once this round is completed, record the above data and move the trainee on to task 2.

Exercise 2: Hand-eye Coordination

The aim of this exercise is to test the trainee's ability to navigate the camera with their non-dominant hand and to simultaneously handle the forceps with their dominant hand.

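### The Task 1–3 layouts are printed in the trainee instruction sheet (Appendix 7) and nothing says they are withheld, so trainees may see the Task 1 search layouts just before being timed

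*Protocol*

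**What the plan says.** The protocol's appendix list names Appendix 7 as the trainees' standardised task instructions, and the appendix itself is headed "Trainee Instructions for laparoscopic tasks". Its exercise texts speak directly to the trainee. After the four exercises and the video links it continues with "Below are the 3 different sequences to be used in task 1" and then "The following are 3 different colour sequences to be used in task 2 and 3". The sections on Tasks 1, 2 and 3 each send the reader to the end of Appendix 7 for these sequences.

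Appendix 13, written for assessors, gives this direction for each of Tasks 1 to 3: "Request the trainee to read the instructions and then show them the demonstration video". It also tells the assessor to mount the inserts according to the numbered sequences, but the text available to us does not reproduce them there.

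On memory, the Task 1 section says: "To avoid memory effect the sequence of targets will be changed each round so that there are 3 different sequences to find". Tasks 2 and 3 carry the parallel statement: "To avoid memory effect the colour sequence of targets will be changed each round". All three sections add: "The same 3 sequences will be used for all trainees throughout the testing phase".

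Under the location and timescale heading the calendar reads: "We will conduct these tasks over 3 weekends (2 consecutive weekends and one weekend 3 weeks later". Each trainee attends one study day, chosen from six.

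**The concern.** Task 1 times a search: the trainee must find 14 targets with the camera as fast as possible, and this time is listed under the primary outcome measure. If a trainee has just looked at a diagram of where the targets lie, part of the recorded time reflects recall and not camera skill. If everyone sees the diagrams, the search component that might separate the specialties or grades is diluted. If only some see them, because assessors hand out the sheet differently, noise is added, and bias too if the handling differs by group.

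There is a second, less certain route. The same layouts serve everyone and trainees choose their own day, so an early attender could describe them to a later one. If one specialty tended to attend later, that would flatter its times. EMG and EEG are recorded in round 2 of Tasks 1 to 3, so foreknowledge could also touch those readings in the 16 monitored trainees (4 in each of 4 groups).

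**Working it through.** The check is mainly textual. The protocol states no figure for this point that could be reproduced.

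**1. Is the sheet with the layouts the sheet trainees read?** The sections on Tasks 1, 2 and 3 say that standardised instructions are given and cite Appendix 7 for them. Appendix 13 has the trainee read the instructions before each task. The same task sections place the sequences at the end of Appendix 7. So the reading material and the layouts share one document.

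**2. Are the layouts separated or withheld anywhere?** No. There is no assessor-only label, no instruction to detach the pages and no request for confidentiality. Appendix 13 relies on the sequences for set-up, and the only stated source for them is the trainee document.

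**3. When could exposure occur?** The Part 2 recruitment email lists only the information sheet and consent form (Appendices 3 and 5) as attachments. Exposure would therefore be on the study day, shortly before timing.

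**4. Which rounds are affected?** There are 3 tasks × 3 rounds = 9 timed rounds in Tasks 1 to 3. In Task 1 the targets must be searched for. In Task 2 the coloured nails are described as easy to see, and in Task 3 the facilitator centres all the targets on the screen. The material risk therefore sits in the 3 Task 1 rounds.

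**5. Does the round-to-round safeguard work?** With 20 + 20 = 40 trainees and 3 rounds each, there are 40 × 3 = 120 Task 1 rounds. Each sequence is used 40 times, once per trainee. Each trainee is invited to one day, so no Task 1 sequence repeats within a trainee and the safeguard works as written. The colour sequences are labelled as common to Tasks 2 and 3, so each trainee meets each of them twice, once per task. This matters little where the targets are in view.

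**6. How long is the window for passing layouts on?** Take the first Saturday as day 0. The second weekend starts on day 7 and the third on day 7 + 21 = 28, ending on day 29. That is about four weeks.

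**7. Size of the bias.** The protocol gives no data on how much prior sight of a layout shortens the search, so this cannot be calculated.

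**The case against.** The strongest reply is that exposure is inferred. The instructions a trainee reads are the exercise texts. The sequences come after all of these and after the video links, and are worded as set-up information. An assessor may well hand over only the exercise text. The diagrams themselves are not visible in the text available to us, so how readily 14 positions in each of three sequences could be memorised from a short reading cannot be judged. This stands, and it is why the point is an open risk and not an established fault.

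A reader might also infer that reusing the same sequences over three weekends defeats the stated aim of avoiding a memory effect. The documents do not support that. The aim concerns memory from one round to the next within a trainee, and step 5 shows that it is met. Common sequences also keep difficulty equal for all trainees and both specialties. What remains is narrower: nothing discourages trainees from passing layouts on. Harm by that route would need leakage, useful recall and a difference in attendance dates between specialties, and the protocol shows none of these.

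A reader might further put a number on the effect. The ideal time gives 150 s / 14 = 10.7 s per target. An assumed saving of 2 to 4 s per target would then be 28 to 56 s per round, or 19% to 37% of 150 s. But the saving has no source in the protocol and could be zero. The 10.7 s also covers zooming, centring the character, reading it out and waiting for the facilitator, none of which prior knowledge shortens. That figure should not be relied on.

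**Conclusion.** The concern holds in limited form. The protocol puts the test layouts in the document that trainees are asked to read before each task and does not say that they are withheld. The material exposure is the three Task 1 rounds, which feed a primary outcome. For Tasks 2 and 3 it is slight, so a reading that all nine rounds are compromised goes too far. The possibility of layouts being passed on over about four weeks is a secondary, unguarded risk and not a contradiction in the plan.

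The conclusion assumes that the diagrams show where the targets sit. That is a fair assumption, since assessors are to mount the inserts from them. The size of any bias is unknown. The point is worth acting on because it protects a primary outcome at almost no cost.

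**What to change.** - Move the sequence diagrams from Appendix 7 to Appendix 13. Alternatively, keep them where they are under a clear label that they are for assessors only and must not be shown to trainees.
- If they are moved, correct the cross-references in the sections on Tasks 1, 2 and 3.
- Add one sentence asking trainees not to discuss the layouts until the last testing weekend is over.
- Keep the same three sequences for all trainees.

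The cost is a relocated set of pages, three cross-references and one sentence.

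As an optional extra, O&G and GS places could be balanced across the weekends where feasible, so that any remaining leakage falls evenly on both specialties. This costs trainees a little free choice of date, and the several weekends are offered precisely to suit on-call duties and leave, so it should not be a condition.

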Runs	Time required for inserting 6 cylinders OR 3 minutes	No of cylinders placed in 3 minutes	No of dropped objects
1	: :		
2	: :		
3	: :		

Task 3: Bimanual co-ordination (BMC)

Runs	Time required for positioning 6 pins OR 3 minutes	No of pins placed in 3 minutes	No of dropped objects
1	: :		
2	: :		
3	: :		

Appendix 9

Scoring sheets for laparoscopic suturing and knot quality:

European
 +theAcademy of
 Gynaecological
 Surgery

SUT+T1 EVALUATION

RESULT			
TIME:	:	:	max 15 min.
DOT:	0	1	2 3 4 5 6 7 8 9 10
CORRECT STITCH:	0	1	2 3 4 5
KNOT:	0 - 2	TRAUMA:	0 1 2

1) TIME

Time maximum - 15 minutes

2) DOT 0-1-2-3-4-5-6-7-8-9-10

To count dots through which the thread is passed correctly.

Dot may be counted when the stitch (thread) is entered in any point of the dot (when the thread is visually in contact with any part of the dot)
 Incorrect dot (not to be counted) is considered when the stitch is passed obviously out of the knot

3) CORRECT STITCH 0 – 5

The thread is passed correctly through **both dots**

4) TRAUMA

The damage of the suturing pad

0 = minimal, no damage | 1 = moderated damage | 2 = heavy damage

5) KNOT 0 – 1 - 2

Flat knot and two additional half knot

2 = knot is correct and tied | 0 = all the rest

Trauma

0: No damage, up to 4 needle puncture marks, no excavation, or exposed foam irrespective of the size of defect.

1: Between 5 and 8 needle puncture marks, defect in foam pad of less than 5mm or extent of trauma more than grade 0 but less than grade 2.

2: More than 8 needle puncture marks, Underlying foam exposed, defect in foam pad of 5mm or more, excavation and cavity formation.

Knot quality:

2: square knot, 3 throws and flat.

0: any of the above absent.

Knot quality should be assessed for each knot. Overall score for this section (knot quality) is the sum of all knots quality scores.

Appendix 10

Electromyography (EMG) protocol

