The aim of this task is to perform 4 interrupted sutures and knots using correct needle handling and intra-corporeal knot tying techniques.

Remove the LASTT model along with its inserts from the box trainer.

A Suturing and knot tying Training and Testing method (SUTT1) foam pad will be used for assessment of suturing and knot placement (Figure 2). This has 5 rows of dots. For this task the top 4 rows are used and the 5th row is disregarded.

[figure not shown]

Figure 2. SUTT1 foam pad for assessment of suturing and intra corporeal knot tying. It contains 5 rows of large black dots placed about 10mm apart.

The suturing pad is affixed on an A4 card labelled SUTT-1. This card is to be secured on to a large black foam base. This foam base has 2 raised edges near the top.

Align the top of A4 SUTT-1 card with the top ridge on this foam base and then secure it on to the foam base using 6 pins (3 pins along each long edge of A4 card).

Attach the large foam base to the floor of the Szabo box trainer using 4 Velcro strips at the four corners. The purpose of this is to prevent any potential movements of the suturing pad/base during the suturing task.

Cut 6 Vicryl 2.0 sutures to a length of 20cm.

As the facilitator you are expected to insert the 0 degrees camera through the central port in the middle of the box trainer. Insert two 5mm lateral ports (left and right) halfway down the box.

Request the trainee to read the instructions and then show them the suturing demonstration video.

Check trainee's understanding of the task.

The trainee is required to perform 4 interrupted sutures by taking a needle bite through the black dots in a horizontal plane. Please instruct the trainee to use the first 4 rows on the suturing pad and leave the 5th row.

The trainee is expected to pass the suture by entering and exiting precisely within the black dots and perform intra-corporeal knot with 3 throws. They should then cut the excess suture using laparoscopic scissors leaving behind a tail of approx. 1-2cm. This process can then be repeated along the 4 rows to perform a total of 4 sutures and 4 knots.

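### Appendix 9 does not say which needle punctures count towards the trauma grade, so a flawless four-suture pad can be graded 0 or 1

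*Protocol*

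**What the plan says.** Task 4 is four interrupted sutures on the top four rows of the foam pad, with a 15-minute limit. The trainee instructions (Appendix 7, Exercise 4) say: "Pass the suture by entering and exiting precisely within the black dots". The assessor information (Appendix 13, Exercise 4) says: "The trainee is required to perform 4 interrupted sutures by taking a needle bite through the black dots in a horizontal plane". The Task 4 section and Appendix 13 both provide for trainees who run out of time: the number of sutures and knots achieved is then recorded. Two independent assessors score the pads afterwards.

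The scoring sheet in Appendix 9 defines the trauma item as "The damage of the suturing pad" and labels its grades "0 = minimal, no damage | 1 = moderated damage | 2 = heavy damage". Below the sheet, a second block gives the working criteria:

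- Grade 0 opens with "0: No damage, up to 4 needle puncture marks" and also requires no excavation or exposed foam.
- Grade 1 opens with "1: Between 5 and 8 needle puncture marks" and ends with a judgement clause, "extent of trauma more than grade 0 but less than grade 2".
- Grade 2 reads "2: More than 8 needle puncture marks, Underlying foam exposed, defect in foam pad of 5mm or more, excavation and cavity formation".

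The Protocol's list of primary outcome measures names the extent of trauma among the Task 4 items.

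**The concern.** The cut-offs refer to puncture marks without qualification, yet the task cannot be done without making punctures. If the required ones are counted, a trainee who does exactly what was asked cannot reach the best grade, and one who stops after two good sutures can. The item would then partly record how many sutures were placed, which the sheet already captures elsewhere.

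If the required punctures are not counted, the rule behaves sensibly, but nothing printed tells the assessor to leave them out. The practical risk is that the two assessors apply different rules to the same pad, or that both apply one that was not intended. An analysis plan could not repair this later, because the sheet records only a grade and not which marks were counted.

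**Working it through.** **Inputs**

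- Sutures required: 4 (Task 4 section; Appendices 7 and 13).
- Marks per suture: 2, one entry and one exit, each in its own dot (Appendix 7). Two dots per row agrees with the sheet's range of 10 dots over 5 rows: 10 / 5 = 2.
- Cut-offs: 0 to 4 marks is grade 0, 5 to 8 is grade 1, 9 or more is grade 2 (Appendix 9).

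**Perfect suturing, no surplus marks.** Let s be the number of sutures placed. The literal count is 2s, the surplus-only count is 0, and the count at one mark per bite is s.

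| Sutures placed | Literal marks | Grade | Surplus-only marks | Grade | One-per-bite marks | Grade |
|---|---|---|---|---|---|---|
| 1 | 2 | 0 | 0 | 0 | 1 | 0 |
| 2 | 4 | 0 | 0 | 0 | 2 | 0 |
| 3 | 6 | 1 | 0 | 0 | 3 | 0 |
| 4 | 8 | 1 | 0 | 0 | 4 | 0 |

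Only the literal count makes the best attainable grade worsen as more sutures are completed. For the complete pad it gives 4 x 2 = 8 marks and grade 1, where the other two rules give grade 0.

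**One surplus mark on a complete pad.** The literal count is 8 + 1 = 9. Appendix 9 does not say whether one grade-2 criterion is enough.

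- If any single criterion is enough, 9 marks gives grade 2.
- If the criteria must occur together, the judgement clause in grade 1 can hold the pad at 1.
- Surplus-only counting gives 1 mark and grade 0.

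The same pad can therefore differ by two grades or by one between the literal and surplus-only rules, depending on how grade 2 is read.

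**Assumptions in this check.** The grades above use puncture count alone, with no excavation, exposed foam or defect. Grade 0 is taken to need all of its listed conditions. If those conditions are alternatives, the literal reading lets the flawless complete pad fit grades 0 and 1 at once.

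**The case against.** The best defence is that no sensible assessor would count the required punctures. The item is about damage, and a hole holding a correct stitch is the purpose of the task. Correct passes are credited separately, by where the thread lies, under the dot and stitch items. The literal rule also looks odd on the sheet's own full range: five perfect stitches would give 5 x 2 = 10 marks and the worst grade. Alternatively, one mark per bite makes the first cut-off of 4 coincide with the four required sutures, and the instructions do speak of needle bites. Every group is graded on the same sheet, and with two assessors a systematic split would be visible.

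Much of this stands. Both alternative readings are plausible, and the conflict with the label for grade 0 arises only on the literal one. What does not stand is that the matter is therefore settled. The text contains no word such as extra or stray, and the station instructions in Appendix 13 give no rule for counting trauma marks. Two plausible readings with different counts still need a choice between them. Disagreement between assessors would show that a problem exists but not which grade was meant, and agreement on an unintended rule would not show at all.

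A reader might infer more: that the rubric penalises trainees who finish, and so biases the comparison of specialties or training grades. The document does not support that. The penalty exists only if required marks are counted. The Protocol gives no completion rates or stray-mark frequencies from which a direction could be derived, and it states no composite score through which this item would affect the others.

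**Conclusion.** The concern holds as an ambiguity in a printed scoring rule. Appendix 9 allows a flawless, complete pad to be graded 0 or 1 according to which marks the assessor counts. With one surplus mark the literal and surplus-only grades differ by one or two steps.

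The consequence is limited. It touches one 0-2 item among several for Task 4; time, dots, correct stitches and knots are unaffected. Any effect on the comparison of specialties or training grades is of unknown direction and size. The point is minor, but worth settling because the item sits under the primary outcome and the remedy is short. The conclusion rests on two marks per suture, which the instructions support, and on the absence of any counting rule in the Protocol as shown. No separate briefing for the two retrospective assessors appears in the document.

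**What to change.** Before scoring, make these changes:

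1. State in Appendix 9 one counting rule under which a correctly completed four-suture pad scores 0. Two candidates are to leave out the entry and exit mark of each placed suture, or to count one mark per needle bite. The sponsor should say which was intended.
2. Have the sponsor confirm that 4 and 8 are the right cut-offs under that rule.
3. State whether any single grade-2 criterion is enough.
4. Give the same text to both retrospective assessors.
5. Report trauma beside the number of sutures placed, since a pad with fewer sutures also offers fewer chances for stray marks.

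The cost is two or three sentences. The number of sutures is already recorded, so the reporting step needs no new data. Scoring takes place after the session on pads that are labelled and collected, so the rule can be fixed without changing the sessions. Pads already graded should be re-scored if they were kept; the Protocol does not say whether they are kept after scoring.
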